12.3 Determination of sample size

The study is sized to estimate the absolute mean difference in IPA with and without the PPI with a specified precision. With 54 healthy volunteers, a 95% CI with length of at most 9 percentage units is achieved with at least 96% probability. With a projected dropout rate of 10%, a total of 59 healthy volunteers will be randomized.

The calculation assumes a SD of paired difference of 14% units, derived from the root mean square error of the analysis of internal data on ADP-induced maximum extent IPA for $^{\circ}$ IPA_{max} (20 μ mol/L).

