5.2.1 Procedures for randomization

A randomization scheme will be generated by Quintiles using the validated global randomization system (GRand). The randomization will be done for 60 subjects in blocks. The healthy volunteers will be randomized to 1 of 2 treatment sequences (A-B and B-A):

- Treatment A: clopidogrel 75 mg once daily for 9 days
- Treatment B: clopidogrel 75 mg for 4 days followed by esomeprazole 20 mg/ASA 81 mg with clopidogrel 75 mg once daily for 5 days

Randomization codes will be assigned strictly sequentially as healthy volunteers become eligible for randomization. With 59 subjects included, this implies the last randomized block not being completely filled (one of the 2 possible permutations will not be used), ie, the last treatment sequence in the randomization list will not be allocated to any subject.

5.3 Procedures for handling subjects incorrectly enrolled or randomized or initiated on investigational product

Healthy volunteers who fail to meet the inclusion or who meet any of the exclusion criteria should not, under any circumstances, be enrolled or randomized. There can be no exceptions to this rule.

Where healthy volunteers that do not meet the selection criteria are randomized in error or incorrectly started on treatment, or where healthy volunteers subsequently fail to meet the study criteria post initiation, a discussion should occur between the AstraZeneca Physician and the Investigator regarding whether to continue or discontinue the healthy volunteer from treatment.

The AstraZeneca Physician is to ensure all such decisions are appropriately documented. In situations where an agreement cannot be reached, the healthy volunteer should have their study therapy stopped.

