5.8.1 Procedures for discontinuation of a subject from the study

Healthy volunteers are at any time free to withdraw from study (IP and assessments), without prejudice to further treatment (withdrawal of consent). Such healthy volunteers will always be asked about the reason(s) and the presence of any AEs. If possible, they will be seen and assessed by an investigator. Adverse events will be followed up (see Sections 6.3.3 and 6.3.4); study drug (including medication log) should be returned by the subject.

Withdrawn healthy volunteers will not be replaced.

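### Section 12.3 is inconsistent by one volunteer: at 10% dropout, 59 randomized gives about 53 completers, not the 54 behind the precision statement

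*Protocol*

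**What the plan says.** Protocol section 12.3 sizes the study on the precision of the mean difference in inhibition of platelet aggregation with and without the PPI, not on power. The target is: "With 54 healthy volunteers, a 95% CI with length of at most 9 percentage units is achieved with at least 96% probability". On variability it says: "The calculation assumes a SD of paired difference of 14% units". It then moves from the number needed to the number randomized: "With a projected dropout rate of 10%, a total of 59 healthy volunteers will be randomized".

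Two other sections bear on this step. Section 5.8.1 states: "Withdrawn healthy volunteers will not be replaced". Section 5.2.1 describes a randomization list made for 60 subjects and explains that, with 59 included, "the last treatment sequence in the randomization list will not be allocated to any subject".

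**The concern.** The number needed, the dropout rate and the number randomized stand together in one short section, so they can be checked against each other. Taking 10% off 59 does not leave 54. The probability in section 12.3 is worded as a floor, and the floor is tied to 54, so it matters whether 54 is what the plan expects to have. Nobody is replaced, so a shortfall would not be made up during the study.

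Section 12.3 gives no power calculation and no equivalence margin. The precision statement is thus the whole stated justification for the sample size, and its figures should agree with each other even where the discrepancy is small.

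**Working it through.** **Inputs, all from Protocol section 12.3 unless noted**
- Number on which the precision rests: n = 54
- Full length of the two-sided 95% CI: L = 9 percentage units
- SD of the paired difference: 14 percentage units
- Stated probability: at least 96%
- Projected dropout: 10%; number randomized: 59
- Replacement: none (section 5.8.1)
- Model: period and treatment as fixed effects, subject within sequence as random (section 12.2.2). For complete pairs this gives n − 2 degrees of freedom; a simple paired analysis gives n − 1. Both are shown.

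**Formula**

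The CI length is 2 × t(0.975, df) × S/√n. It is at most 9 when S ≤ 9√n/(2t). Because df × S²/14² follows a chi-square distribution with df degrees of freedom,

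P(length ≤ 9) = P(χ²_df ≤ df × [9√n/(2 × t × 14)]²).

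**Step 1: reproduce the protocol's figure at n = 54**
- df 53: t = 2.0057, largest allowed S = 16.49, chi-square limit 73.50, P = 96.7%
- df 52: t = 2.0066, largest allowed S = 16.48, chi-square limit 72.05, P = 96.6%

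The stated floor of 96% is reproduced under either choice.

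**Step 2: from the number needed to the number randomized**
- Expected completers from 59: 59 × 0.90 = 53.1, about 53
- Number to randomize for 54 completers: 54/0.90 = 60
- Dropout rate at which 59 gives 54: 1 − 54/59 = 8.5%

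**Step 3: the probability at n = 53**
- df 52: t = 2.0066, largest allowed S = 16.33, chi-square limit 70.71, P = 95.7%
- df 51: t = 2.0076, largest allowed S = 16.32, chi-square limit 69.29, P = 95.5%

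Both are below 96%, by 0.3 and 0.5 points. Of the two, 54 is the smallest n that meets the floor.

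**Step 4: dropout as a random number**

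If each of 59 volunteers completes independently with probability 0.90, the chance of at least 54 completers is 45%. Averaging the probability in the formula over the binomial number of completers gives 95.1% (df n − 1) or 94.9% (df n − 2). For comparison, 60 randomized gives a 61% chance of at least 54 completers and an average of 96.1% or 96.0%.

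**Step 5: the same gap in units of CI length**

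The length not exceeded with 96% probability at n = 53 is 9.03 (df 52) or 9.05 (df 51), against the target of 9. With S equal to 14, the CI length is 7.64 at n = 54 and 7.72 at n = 53.

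**The case against.** The strongest reply is that the gap is smaller than the accuracy of the inputs. The SD is a rounded figure taken from internal data: with an SD of 13.9, 53 completers give 96.4% (df 52), while with 14.2 even 54 completers give only 95.4% (df 53). The dropout rate is only projected, and 8.5% could pass for a rounded 10%. The sentence about 54 volunteers is correct as it stands and is conditional on 54; section 12.3 does not claim that its probability averages over dropout. In addition, the pharmacodynamic analysis set in section 12.1.3 asks for at least one suitable post-dose assessment, so a volunteer who leaves after period 1 may add a little information through the mixed model.

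All of this stands as a statement about size. None of it reconciles the figures: at the stated SD and dropout rate, the stated number randomized does not lead to the number on which the floor rests. The sizing is built on paired differences, and the amount recovered from single-period data cannot be worked out from the protocol.

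Three stronger readings are tempting but not supported:
- A reader might infer that the trial will lack its planned precision. A length of 9.03 to 9.05 instead of 9 does not bear that out.
- A reader might see the unused last code, and the 30/29 sequence split that follows, as a design fault. Section 5.2.1 discloses and explains it as a choice. The variance of the treatment contrast rises by a factor of 59²/(4 × 30 × 29) = 3481/3480, about 0.03%, and period is in the model.
- A reader might conclude that 59 came from 54 × 1.10 = 59.4. That fits, but the protocol shows no inflation formula, so it remains a guess.

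**Conclusion.** Section 12.3 is internally inconsistent by one volunteer. With 10% dropout and no replacement, 59 randomized gives about 53 completers, and the probability of a CI no longer than 9 units is then about 95.5 to 95.7%, or about 95% averaged over random dropout, slightly under the stated floor of 96%. This rests on the protocol's SD of 14, on t-based intervals from complete pairs, and, for the averaged figure, on independent dropout at 10%. The precision statement for 54 volunteers is itself right; only the step from 54 to 59 is off. The matter is minor: it calls for a correction of the text and does not put the trial's conclusions in doubt.

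**What to change.** Change one sentence in section 12.3, in either of two ways:
- Keep 10% dropout and state the consequence: 59 randomized, about 53 expected completers, 95% CI length at most 9 percentage units with about 95% probability.
- Keep 54 completers and the 96% floor, and state the projected dropout as about 8.5%, if the sponsor considers that rate realistic.

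Either costs a line of text and leaves the conduct of the study unchanged. The first makes the stated probability slightly less favourable; the second commits the plan to a lower dropout rate.

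Allocating the 60th code already on the list is optional. It would give 60 × 0.90 = 54 expected completers, at the cost of one more volunteer and a change from 59 to 60 in the synopsis and sections 3.1, 5.2.1 and 12.3. The size of the discrepancy does not require it.

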13.2 Overdose

The symptoms described in connection with deliberate esomeprazole overdose (limited experience of doses in excess of 240 mg/day) are transient. Esomeprazole is extensively plasma protein bound and is therefore not readily dialyzable. As in any case of overdose, treatment should be symptomatic and general supportive measures should be utilized. Refer to the "Overdose" section of the official prescribing information at: http://www1.astrazeneca-us.com/pi/Nexium.pdf

Symptoms associated with ASA overdose include: vertigo, tinnitus, auditory impairment, hyperactivity, irritation, hallucinosis, tremor, asterixis, hyperventilation, thirst, erythema of the skin, hyperhidrosis, nausea, vomiting, and abdominal pain. Symptoms of severe intoxication with ASA include: unconsciousness, convulsions, and hyperthermia. As in any case of overdose, treatment should be symptomatic and general supportive measures should be utilized.

Clopidogrel- refer to the "Overdose" section of the official prescribing information at: http://products.sanofi-aventis.us/PLAVIX/PLAVIX.html

If an overdose on an AstraZeneca study drug occurs in the course of the study, then investigators or other site personnel inform appropriate AstraZeneca representatives within 1 day, ie, immediately but no later than the end of the next business day of when he or she becomes aware of it.

The designated AstraZeneca representative works with the investigator to ensure that all relevant information is provided to the AstraZeneca Patient Safety data entry site.

For overdoses associated with SAE, standard reporting timelines apply, see Section 6.3.4. For other overdoses, reporting should be done within 30 days.

13.3 Pregnancy

All outcomes of pregnancy should be reported to AstraZeneca.

Females of childbearing potential must adhere to the birth control methods outlined in Section 4.1. If the Investigator receives information that a pregnancy has occurred during the study despite these restrictions, the designated Quintiles representative should be informed.


Appendix B Additional Safety Information

FURTHER GUIDANCE ON THE DEFINITION OF A SERIOUS ADVERSE EVENT (SAE)

Life threatening

'Life-threatening' means that the subject was at immediate risk of death from the AE as it occurred or it is suspected that use or continued use of the product would result in the subject's death. 'Life-threatening' does not mean that had an AE occurred in a more severe form it might have caused death (eg, hepatitis that resolved without hepatic failure).

Hospitalisation

Outpatient treatment in an emergency room is not in itself a serious AE, although the reasons for it may be (eg, bronchospasm, laryngeal oedema). Hospital admissions and/or surgical operations planned before or during a study are not considered AEs if the illness or disease existed before the subject was enrolled in the study, provided that it did not deteriorate in an unexpected way during the study.

Important medical event or medical intervention

Medical and scientific judgement should be exercised in deciding whether a case is serious in situations where important medical events may not be immediately life threatening or result in death, hospitalisation, disability or incapacity but may jeopardize the subject or may require medical intervention to prevent one or more outcomes listed in the definition of serious. These should usually be considered as serious.

Simply stopping the suspect drug does not mean that it is an important medical event; medical judgement must be used.

Examples of such events are:

- Angioedema not severe enough to require intubation but requiring iv hydrocortisone treatment
- Hepatotoxicity caused by paracetamol (acetaminophen) overdose requiring treatment with N-acetylcysteine
- Intensive treatment in an emergency room or at home for allergic bronchospasm
- Blood dyscrasias (eg, neutropenia or anaemia requiring blood transfusion, etc) or convulsions that do not result in hospitalisation
- Development of drug dependency or drug abuse.

A GUIDE TO INTERPRETING THE CAUSALITY QUESTION

The following factors should be considered when deciding if there is a "reasonable possibility" that an AE may have been caused by the drug.

- Time Course. Exposure to suspect drug. Has the subject actually received the suspect drug? Did the AE occur in a reasonable temporal relationship to the administration of the suspect drug?
- Consistency with known drug profile. Was the AE consistent with the previous knowledge of the suspect drug (pharmacology and toxicology) or drugs of the same pharmacological class? OR could the AE be anticipated from its pharmacological properties?
- Dechallenge experience. Did the AE resolve or improve on stopping or reducing the dose of the suspect drug?
- No alternative cause. The AE cannot be reasonably explained by another aetiology such as the underlying disease, other drugs, other host or environmental factors.
- Rechallenge experience. Did the AE reoccur if the suspected drug was reintroduced after having been stopped? AstraZeneca would not normally recommend or support a rechallenge.
- Laboratory tests. A specific laboratory investigation (if performed) has confirmed the relationship?

A "reasonable possibility" could be considered to exist for an AE where one or more of these factors exist.

In contrast, there would not be a "reasonable possibility" of causality if none of the above criteria apply or where there is evidence of exposure and a reasonable time course but any dechallenge (if performed) is negative or ambiguous or there is another more likely cause of the AE.

In difficult cases, other factors could be considered such as:

- Is this a recognised feature of overdose of the drug?
- Is there a known mechanism?

Ambiguous cases should be considered as being a "reasonable possibility" of a causal relationship unless further evidence becomes available to refute this. Causal relationship in cases where the disease under study has deteriorated due to lack of effect should be classified as no reasonable possibility.

Clinical Study Protocol Appendix C

Drug Substance Esomeprazole 20 mg/ASA 81 mg

Study Code D961FC00010

Edition Number 1

Date

Appendix C International Airline Transportation Association (IATA) 6.2 Guidance Document

LABELLING AND SHIPMENT OF BIOHAZARD SAMPLES

International Airline Transportation Association (IATA) classifies biohazardous agents into 3 categories (http://www.iata.org/whatwedo/cargo/dangerous_goods/infectious_substances. htm). For transport purposes the classification of infectious substances according to risk groups was removed from the Dangerous Goods Regulations (DGR) in the 46th edition (2005). Infectious substances are now classified either as Category A, Category B or Exempt. There is no direct relationship between Risk Groups and categories A and B.

Category A Infectious Substances are infectious substances in a form that, when exposure to it occurs, is capable of causing permanent disability, life-threatening or fatal disease in otherwise healthy humans or animals. Category A pathogens are eg, Ebola, Lassa fever virus:

• are to be packed and shipped in accordance with IATA Instruction 602.

Category B Infectious Substances are infectious Substances that do not meet the criteria for inclusion in Category A. Category B pathogens are eg, Hepatitis A, B, C, D, and E viruses, Human immunodeficiency virus (HIV) types 1 and 2. They are assigned the following UN number and proper shipping name:

- UN 3373 Biological Substance, Category B
- are to be packed in accordance with UN3373 and IATA 650

Exempt - all other materials with minimal risk of containing pathogens

- Clinical trial samples will fall into Category B or exempt under IATA regulations
- Clinical trial samples will routinely be packed and transported at ambient temperature in IATA 650 compliant packaging
 (http://www.iata.org/whatwedo/cargo/dangerous_goods/infectious_substances.htm)
- Biological samples transported in dry ice require additional dangerous goods specification for the dry-ice content
- IATA compliant courier and packaging materials should be used for packing and transportation and packing should be done by an IATA certified person, as applicable

• Samples routinely transported by road or rail are subject to local regulations which require that they are also packed and transported in a safe and appropriate way to contain any risk of infection or contamination by using approved couriers and packaging / containment materials at all times. The IATA 650 biological sample containment standards are encouraged wherever possible when road or rail transport is used.
